7.1.1. Packaging and Labeling

Clinical trial materials will be labeled according to the regulatory requirements. LY3298176 and the matched placebos will be supplied by Lilly. CCI

CCI [REDACTED] Patients will inject the dose volume appropriate for their treatment group, including placebo patients within a group. LY3298176 vials must always be stored in a secure location with access limited to designated study staff members.

Instructions for the reconstitution of study drug will be provided separately to each patient and the investigator. CCI [REDACTED]

[REDACTED] The reconstituted LY3298176 or placebo solution should be used immediately after reconstitution.

Study drug must be stored in a refrigerator at 2°C to 8°C (36°F to 46°F). Temperature logs must be maintained to verify correct storage conditions at the investigator site, throughout the study. Patients should be instructed to store the study drug in their refrigerator but are not required to maintain temperature logs. Sterile water vials may be stored at room temperature.

7.1.2. Medical Devices

The manufactured medical devices provided for patient use in the study are glucose meters and lancet devices.

7.2. Method of Treatment Assignment

A unique 4-digit patient number will be assigned to each patient when the patient signs the ICF.

Patients will be assigned to placebo or 1 of 3 LY3298176 titration groups. Patients who meet all criteria for enrollment will be randomized at Visit 3 and assigned to their respective treatment arms via IWRS using the following stratification variables: baseline HbA1c (<8.5%, ≥8.5%), metformin use (Yes, No), and BMI (<30, ≥30). There will be approximately an equal randomization to the treatment arms (1:1:1).

The randomization algorithm will be performed using IWRS that will ensure balance between treatment arms.

7.2.1. Selection and Timing of Doses

Assignment to 1 of 3 LY3298176 titration groups or placebo will occur at randomization. There are no restrictions on the time of day each QW dose is given, but it is advisable to administer SC injections on the same day and same time each week. Patients should be instructed to record the actual date and time of all dose administrations in the diary provided. The actual date and time of all dose administrations will be recorded in the subject's case report form (CRF). If a dose of study drug, including placebo, is missed, the patient should take it as soon as possible and contact the study site for further instructions on timing of the next scheduled dose.

7.2.2. Specific Restrictions/Requirements

Prior to beginning the study, patients will complete informed consent and baseline tests.

Throughout the study, patients may undergo medical assessments and compliance reviewed before continuing in the study.

Patients will report to the clinical research site for safety assessments and will remain in the clinic until all procedures for that visit are complete and the investigator has deemed it safe to release the patient from the clinic. There will be no inpatient stays.

Meals/Diet – Patients shall fast for at least 8 hours overnight prior to each outpatient visit where fasting samples are drawn or weight measurements taken.

Alcohol – Alcohol will not be permitted 8 hours prior to the dosing day, until the patient has been discharged from the clinical research site.

Exercise – Patients will be advised to maintain their regular levels of physical activity/exercise during the study. When certain study procedures are in progress at the site, patients may be required to remain recumbent or sitting.

Blood donation – Study participants should be instructed not to donate blood or blood products during the study or for 8 weeks following the study.

Contraception – Male patients or their female partners of child-bearing potential must use reliable contraception during intercourse throughout the treatment period and for 3 months after the last dose of study drug as the risk of LY3298176 to the unborn fetus is unknown. Female patients of child-bearing potential, if sexually active, should use 2 forms of effective contraception, where at least 1 form is highly effective for the duration of the trial and for 30 days thereafter. Please see [Appendix 6](#) for further details regarding contraception.

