6.1. Inclusion Criteria

Patients are eligible to be included in the study only if they meet all of the following criteria at screening:

Type of Patient and Disease Characteristics

- [1] Have T2DM for at least 6 months before screening based on the disease diagnostic criteria ([Appendix 5](#)).
- [2] Have an HbA1c value at screening of $\geq 7.0\%$ and $\leq 10.5\%$ and treated with diet and exercise alone or a stable dose of metformin (either immediate release or extended release, ≥ 1000 mg/day and not more than the locally approved dose) for at least 3 months prior to screening/Visit 1.

Patient Characteristics

- [3] Male or female patients 18 to 75 years of age, inclusive.

[3a] Male patients:

Male patients should be willing to use reliable contraceptive methods throughout the study and for at least 3 months after last injection (see [Appendix 6](#)).

[3b] Female patients:

Women not of child-bearing potential may participate and include those who are:

- infertile due to surgical sterilization (hysterectomy, bilateral oophorectomy, or tubal ligation), congenital anomaly such as mullerian agenesis; or
- postmenopausal – defined as
 - A woman at least 50 years of age with an intact uterus, not on hormone therapy, who has had either cessation of menses for at least 1 year; or
 - at least 6 months of spontaneous amenorrhea with a follicle-stimulating hormone (FSH) >40 mIU/mL; or
 - A woman 55 or older not on hormone therapy, who has had at least 6 months of spontaneous amenorrhea; or
 - A woman at least 55 years of age with a diagnosis of menopause prior to starting hormone replacement therapy.

Women of child-bearing potential (not surgically sterilized and between menarche and 1-year postmenopausal) may participate. In order to participate, they must:

- Women of child-bearing potential who are abstinent (if this is complete abstinence, as their preferred and usual lifestyle) or in a same sex relationship (as part of their preferred and usual lifestyle) must agree to either remain abstinent or stay in a same sex relationship without sexual relationships with males.
- Otherwise, women of child-bearing potential participating must agree to use 1 highly effective method (<1% failure rate) of contraception, or a combination of 2 effective methods of contraception for the entirety of the study:

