 - Women of child-bearing potential must test negative for pregnancy prior to initiation of treatment as indicated by a negative serum pregnancy test at the screening visit and followed by a negative urine pregnancy test within 24 hours prior to exposure. (Any pregnancy testing subsequent to this initial test should be based on compound specific concerns and is not mandated by this guidance.)
 - Either 1 highly effective method of contraception (such as combination oral contraceptives, implanted contraceptives, or intrauterine device) or a combination of 2 effective methods of contraception (such as male or female condoms with spermicide, diaphragms with spermicide, or cervical sponges) will be used. The subject may choose to use a double barrier method of contraception. Barrier protection methods without concomitant use of a spermicide are not a reliable or acceptable method. Thus, each barrier method must include use of a spermicide. It should be noted that the use of male and female condoms as a double barrier method is not considered acceptable due to the high failure rate when these methods are combined.
- Not be breastfeeding.

[4] Have a body mass index (BMI) between 23 and 45 kg/m² (inclusive) at screening.

Informed Consent

[5] In the investigator's opinion, are well motivated, capable, and willing to:

- prepare (with assistance if necessary) study medication
- self-inject (with assistance if necessary) up to 3 injections each week
- complete study diary(ies), as required for this protocol
- are receptive to continuing their prestudy diet, activity levels, and follow simple dietary advice as appropriate
- perform SMBG using the provided glucose meter.

[6] Be willing to maintain metformin dose during the trial, if taking a stable dose of metformin at study entry. Patients experiencing hypoglycemia during the study may have their metformin dose reduced.

- [7] Are reliable and willing to make themselves available for the duration of the study, and who will comply with the required study and dosing visits and abide by the clinical research site policy and procedure and study restrictions.
- [8] Are able and willing to give signed informed consent and have given written informed consent to participate in this study in accordance with local regulations and the ethical review board (ERB) governing their site.

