Appendix 6. Contraceptive Methods

Men

Male patients with female partners of child-bearing potential will be required to use a condom in conjunction with a spermicidal gel, foam, cream, or suppository. In addition, the female partner, will be requested to use an additional effective form of contraception, which can be any of the following:

- diaphragm with spermicide
- cervical sponge
- cervical cap with spermicide
- combined oral contraceptive pill and mini-pill
- NuvaRing
- implantable contraceptives
- injectable contraceptives (such as Depo-Provera®)
- intrauterine device (such as Mirena® and ParaGard®)
- true abstinence, when in line with the preferred and usual lifestyle of the patient.

Men who have had a vasectomy with appropriate postvasectomy documentation of the absence of sperm in the ejaculate are not required to use contraception. In addition, Inclusion Criterion 3b (Section 6.1) provides a specific definition of women not of child-bearing potential; these subjects will not be required to use contraception. Male patients with a female partner meeting the definition of a woman not of child-bearing potential will not be required to use contraception.

Women of Child Bearing Potential

Women of child-bearing potential will be required to use contraception, which can be any of the following:

- Abstinence: If this is complete abstinence, as their preferred and usual lifestyle or in a same sex relationship (as part of their preferred and usual lifestyle) must agree to either remain abstinent or stay in a same sex relationship without sexual relationships with males.
- Birth Control: Use of 1 highly effective method (<1% failure rate) of contraception, or a combination of 2 effective methods of contraception for the entirety of the study:
 - Either 1 highly effective method of contraception (such as combination oral contraceptives, implanted contraceptives, or intrauterine device)
 - A combination of 2 effective methods of contraception (such as male or female condoms with spermicide, diaphragms with spermicide, or cervical sponges) will be used. The subject may choose to use a double barrier method of contraception. Barrier protection methods without concomitant use of a spermicide are not a reliable or acceptable method. Thus, each barrier method must include use of a spermicide.

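### Section 7.2.2 asks sexually active women of child-bearing potential for a stricter set of contraceptive methods than inclusion criterion 3b and Appendix 6, and adds 30 days they do not mention

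*Protocol*

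**What the plan says.** Three places in the Protocol state what women of child-bearing potential are to do.

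- **Section 6.1, criterion 3b.** Women who are neither abstinent nor in a same-sex relationship "must agree to use 1 highly effective method (<1% failure rate) of contraception, or a combination of 2 effective methods of contraception", and the period given is the whole study. The criterion then repeats the rule with examples: "Either 1 highly effective method of contraception (such as combination oral contraceptives, implanted contraceptives, or intrauterine device) or a combination of 2 effective methods". The examples for the two-method option are barrier products, "such as male or female condoms with spermicide, diaphragms with spermicide, or cervical sponges".
- **Section 7.2.2.** Its scope and force are set by the words "Female patients of child-bearing potential, if sexually active, should use". What it then asks for is "2 forms of effective contraception, where at least 1 form is highly effective for the duration of the trial and for 30 days thereafter". The paragraph closes by pointing to Appendix 6 "for further details regarding contraception".
- **Appendix 6.** It offers women a list of acceptable options. Apart from abstinence or a same-sex relationship, the option is "Use of 1 highly effective method (<1% failure rate) of contraception, or a combination of 2 effective methods of contraception for the entirety of the" (the phrase ends with the word study). This is the rule of 3b, not that of Section 7.2.2.

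For men, criterion 3a and Section 7.2.2 agree on a period of 3 months after the last injection or dose.

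**The concern.** Section 7.2.2 joins two conditions (two forms, and at least one of them highly effective). Criterion 3b and Appendix 6 offer alternatives (one highly effective method, or two effective ones). A site that reads Section 7.2.2 and follows its cross-reference arrives at a rule that permits what Section 7.2.2 does not.

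What is at stake is protection against pregnancy during and after exposure. Section 7.2.2 describes the risk to the unborn fetus as unknown. That sentence concerns male patients and their partners, but the drug is the same. Pregnancy leads to permanent discontinuation of study drug (Section 8.1.1) and is reported through the SAE process (Section 9.2.1). The SAP's Appendix 2 lists a positive pregnancy test as an important deviation that needs immediate notification. Two sites could counsel women differently and both cite the Protocol.

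**Working it through.** No sample size, power or event figure is involved. The check applies each rule to the possible cases and then compares the durations.

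**Methods, for a sexually active woman of child-bearing potential with a male partner**

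| Method used | Criterion 3b | Appendix 6 | Section 7.2.2 |
|---|---|---|---|
| One highly effective method alone (e.g. intrauterine device) | meets | meets | does not meet |
| Two effective methods, neither highly effective (e.g. diaphragm with spermicide plus cervical sponge) | meets | meets | does not meet |
| Two forms, at least one highly effective | meets | meets | meets |
| One effective method that is not highly effective | does not meet | does not meet | does not meet |

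The rules disagree in the first two rows. In the first the number of methods differs (one against two). In the second the number is the same and only the type differs. The disagreement runs one way: no combination satisfies the method rule of Section 7.2.2 and fails that of 3b.

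**Who is outside the method conflict.** Abstinent women are provided for in 3b and Appendix 6, and Section 7.2.2 is limited to those who are sexually active. There is a smaller mismatch of scope: 3b and Appendix 6 also exempt women in a same-sex relationship, whereas the wording of Section 7.2.2 would include them if sexually active.

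**Duration.** Inputs from the Schedule of Activities and Table GPGF.3: Dose 12 falls at Week 11, which is day 11 × 7 = 77, and Visit 801 is on day 105.

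- Criterion 3b, if a woman's study ends at Visit 801: 105 − 77 = 28 days after the last dose.
- Section 7.2.2, on the same reading of when the trial ends: 28 + 30 = 58 days after the last dose.

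Both figures assume that study and trial mean the individual woman's participation. Section 5.3 defines the end of the trial by the last patient. On that clock the period in Section 7.2.2 would be longer for women enrolled early, by an amount that cannot be worked out because the enrolment period is not given. The men's rule is counted from the last dose and has no such ambiguity.

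**The case against.** The best defence is that Section 7.2.2 adds a stricter layer on top of the entry criterion. It says should for women, where the sentence before it says must for men. A woman who follows it also satisfies the method rule of 3b, so nobody is given instructions that cannot both be met. The 30 days can likewise be read as an addition, since 3b is silent on the period after the study. Pregnancy testing at screening and before the first dose does not depend on which rule is used, and the SAP's list of important deviations has no item for contraceptive method.

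Much of this stands. The duration difference is an added period, not a flat contradiction. The end of Appendix 6 was not in the text available, so it cannot be confirmed that the appendix is silent on a period after the study.

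The defence does not remove the method conflict. Section 7.2.2 is headed as restrictions and requirements, and it refers for its details to an appendix that expressly allows options falling short of it.

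A reader might infer that eligibility would differ between sites, that every enrolled woman of child-bearing potential is affected, or that the consent form is also inconsistent. The documents support none of these. Section 6.1 ties eligibility to meeting its own criteria and Section 7.2.2 is not one of them, so a woman who meets 3b is not made ineligible by Section 7.2.2. Only the first two rows of the table are in conflict. The consent pages were not available.

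**Conclusion.** The inconsistency is real and visible in the text. On methods, Section 7.2.2 disagrees both with criterion 3b and with the appendix it cites. It affects sexually active women of child-bearing potential who use one highly effective method alone, or two effective methods with neither highly effective. Their number is not stated. On duration, Section 7.2.2 adds 30 days that 3b and the readable part of Appendix 6 do not mention. That is about 58 against 28 days after the last dose if a woman's study ends at Visit 801.

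The consequence is inconsistent counselling during and after exposure. It has no bearing on randomization, sample size, power or the primary analysis. This is a minor wording error that bears on participant safety. Nothing here judges which of the rules is right.

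**What to change.** Reconcile Section 6.1 (criterion 3b), Section 7.2.2 and Appendix 6 to one statement, with the other two places referring to it. The statement should settle:

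- the number and type of methods;
- how long contraception is to be used;
- the point from which that period is counted (last dose, the woman's last visit, or end of trial);
- which women it covers, including those in a same-sex relationship;
- whether it is a requirement or advice.

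The clinical team should decide which rule applies. The cost is a wording change to the Protocol, plus a check that the consent form matches the chosen text. No design feature or analysis changes.

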7.3. Blinding

This is a double-blind study. Although the patient and the investigator will know which dose titration group (Group 1, Group 2, or Group 3) the patient is assigned to, they will not know whether the patient is receiving LY3298176 or placebo.

To preserve the blinding of the study, a minimum number of Lilly personnel will see the randomization table and treatment assignments before the study is complete.

Emergency codes, generated by a computer drug-labeling system, will be available to the investigator. These codes, which reveal the patient's treatment group when opened, may be opened during the study ONLY if the patient's well-being requires knowledge of the patient's treatment assignment.

Emergency unblinding for AEs may be performed through the IWRS, which may supplement or take the place of emergency codes generated by a computer drug-labeling system. This option may be used ONLY if the patient's well-being requires knowledge of the patient's treatment assignment. All calls resulting in an unblinding event are recorded and reported by the IWRS.

If an investigator, site personnel performing assessments, or patient is unblinded, the patient must be discontinued from the study. In cases where there are ethical reasons to have the patient

remain in the study, the investigator must obtain specific approval from a Lilly clinical research physician (CRP)/clinical research scientist (CRS) for the patient to continue in the study.

In case of an emergency, the investigator has the sole responsibility for determining if unblinding of a patient's treatment assignment is warranted for medical management of the event. Patient safety must always be the first consideration in making such a determination. If a patient's treatment assignment is unblinded, Lilly must be notified immediately. If the investigator decides that unblinding is warranted, it is the responsibility of the investigator to promptly document the decision and rationale and notify Lilly as soon as possible.

Upon completion of the study, all codes must be returned to Lilly or its designee.

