HbA1c	X		X			X		X		X	X	X
Fasting glucose	X		X			X		X		X	X	X
Total and active GLP-1/GIP			X			X		X		X	X	
7-point SMBG			X ¹							X ^j		
PK ^k						X		X		X	X	X
Immunogenicity			X			X		X		X	X ¹	X
Nonpharmacogenetic stored samples			X							X		

Abbreviations: AE = adverse event; BG = blood glucose; BP = blood pressure; ECG = electrocardiogram; eGFR = estimated glomerular filtration rate; ET = Early Termination; FSH = follicle-stimulating hormone; GLP-1 = glucagon-like peptide-1; GIP = glucose-dependent insulinotropic peptide; HbA1c = hemoglobin A1c; IWRS = interactive web response system; LH = luteinizing hormone; PK = pharmacokinetics; PR = pulse rate; SMBG = self-monitoring of blood glucose; T = telephone visit; TE = treatment emergent; Term. = termination.

- a Telephone visits occur during the week following a dose escalation and should be done 3 to 6 days after a site visit for dose escalation and administration. At telephone visits, the sites should call the patient, ask how the patient is, and ask whether the patient would like to come to the site for assistance with the next study drug dilution and administration. Sites should also remind patients to write down any AEs in their diaries at the telephone visits (as well as at all site visits).
- b Visit should occur approximately 1 week after the last dose (Dose 12).
- c Additional physical examinations may be performed throughout the study if determined necessary due to patient symptoms.
- d Visit should occur 4 weeks after the last dose of study drug or 3 weeks after Visit 10.
- e ECGs should be collected prior to all blood draws and study drug administrations. Local ECGs will be collected for screening (Visit 1) and Early Termination. Centralized ECGs, collected in supine position and in triplicate, should be collected for all other designated visits.
- f Screening laboratory tests include serum hepatitis B surface Ag, hepatitis C antibody (Ab), and human immunodeficiency virus (HIV) Ab tests for all patients (see Appendix 2).
- g Serum pregnancy test will be performed by central laboratory at Visit 1 for women of child-bearing potential. For the remainder of the study, a urine pregnancy test may be performed at the investigator's discretion if pregnancy is suspected during the study (local laboratory). A urine pregnancy test (local) should be given to all women of child-bearing potential at Visit 3 prior to administration of first dose of study drug to confirm lack of pregnancy.

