Patients who develop severe, persistent hyperglycemia based on prespecified thresholds (see Section [9.2.1.2.4](#)) will receive a new glucose-lowering intervention (or rescue therapy) based on clinical judgment of the investigator, and the patient will discontinue study drug. Patients who need rescue therapy for this reason will be asked to remain in the trial until they complete all study visits for collection of safety information. Patients who discontinue study drug due to AEs will also be asked to continue in the trial for collection of safety information. Patients who are unable or unwilling to continue in the study because of an AE or any other reason will perform

an early termination (ET) visit as their final study visit. If the patient is discontinuing during an unscheduled visit, that visit should be performed as the ET visit. If the patient is discontinuing during a scheduled visit, that visit should be considered the ET visit. At this visit, patients will perform procedures listed in the Schedule of Activities (Section 2).

Study Period III (Safety Follow-Up, Visit 801):

All randomized patients who complete the treatment period will complete the safety follow-up approximately 4 weeks after their last visit on treatment.

Patients randomized to LY3298176 who have treatment-emergent anti-LY3298176 antibodies or antibodies to native GIP or GLP-1 at the last visit may be monitored after the last visit (see Section 9.9).

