- If the patient, for any reason (including protocol-mandated institution of rescue therapy; see Section 7.8.1), requires treatment for >1 week with another therapeutic agent that has been demonstrated to be effective for treatment of diabetes. Also, a change in dose of metformin is not allowed (except for incidences of hypoglycemia; see Section 7.1). However, a change to an equivalent dose strength from immediate-release to extended-release (or vice versa) formulation is allowed.
- If the patient misses ≥ 2 doses (consecutive or not) of study medication or intentionally or repeatedly takes more than the prescribed dose of study medication (see Section 9.3).
- If the patient develops any exclusion criteria, such as pregnancy or nursing.

If study drug is permanently discontinued, the patient should remain in the study if possible. Patients discontinuing from the investigational product prematurely for any reason should complete adverse event and other follow-up procedures per Section 2 (Schedule of Activities), Section 9.2 (Adverse Events), and Section 9.4 (Safety) of this protocol.

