9.2.1.2.5. Acute Pancreatitis

Acute pancreatitis is defined as an AE of interest for this study. Acute pancreatitis is an acute inflammatory process of the pancreas that may also involve peripancreatic tissues and/or remote organ systems (Banks et al. 2006). The diagnosis of acute pancreatitis requires 2 of the following 3 features:

- abdominal pain, characteristic of acute pancreatitis (generally located in the epigastrium and radiates to the back in approximately half the cases [Banks et al. 2006; Koizumi et al. 2006]; the pain is often associated with nausea and vomiting);
- serum amylase (total and/or pancreatic) and/or lipase $\geq 3 \times$ ULN;
- characteristic findings of acute pancreatitis on computed tomography (CT) scan or magnetic resonance imaging (MRI).

If acute pancreatitis is suspected, appropriate laboratory tests (including levels of pancreatic amylase and lipase) should be obtained via the central laboratory (and locally, if needed). Imaging studies, such as abdominal CT scan with or without contrast, MRI, or gallbladder ultrasound, should be performed. If laboratory values and/or abdominal imaging support the diagnosis of acute pancreatitis, the patient must discontinue therapy with investigational product, but will continue in the study on another glucose-lowering regimen (see Section 7.8.1 for details on rescue intervention). The most appropriate diabetes therapeutic regimen will be decided by the investigator, based on the patient's clinical status. A review of the patient's concomitant medications should be conducted to assess any potential causal relationship with pancreatitis.

Each case of AE of pancreatitis must be reported. If typical signs and/or symptoms of pancreatitis are present and confirmed by laboratory values (lipase or amylase [total and/or pancreatic]) and imaging studies, the event must be reported as an SAE. For a potential case that does not meet all of these criteria, it is up to the investigator to determine the seriousness of the case (AE or SAE) and the relatedness of the event to study drug.

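### Protocol 7.3 makes leaving the study, not only stopping study drug, the default after unblinding, out of line with how the protocol treats patients who stop drug

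*Protocol*

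**What the plan says.** Protocol 7.3 lets emergency codes be opened only when the patient's well-being depends on knowing the assignment. It then sets the consequence of any unblinding, emergency or not: "If an investigator, site personnel performing assessments, or patient is unblinded, the patient must be discontinued from the study". The one exception needs ethical reasons and specific sponsor CRP/CRS approval. The rule concerns study participation and does not treat study drug separately.

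For patients who stop study drug, the protocol points towards retention:

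- Section 5.1: "Patients who discontinue study drug due to AEs will also be asked to continue in the trial for collection of safety information".
- Section 8.1.1: "If study drug is permanently discontinued, the patient should remain in the study if possible".
- Section 8.1.2 allows the patient to go on with all visits and procedures.
- Section 9.2.1.2.3 says that a patient taken off drug for a hypersensitivity reaction should stay in.
- Section 9.2.1.2.5, once tests support acute pancreatitis: "the patient must discontinue therapy with investigational product, but will continue in the study on another glucose-lowering regimen".

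For patients who do leave, the Schedule of Activities provides an ET visit, and Section 8.2 asks for adverse event and other safety follow-up. In the SAP, the primary analysis uses the efficacy analysis set (EAS), which drops data after rescue or beyond last dose plus 7 days (Table 6.2). Supporting analyses use the full analysis set (FAS) (6.9.1.1).

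**The concern.** Breaking the blind is a reason to question continued dosing and later subjective assessments. It is not in itself a reason to stop observing the patient, and leaving the study does not restore the blind. Emergency code breaks arise from a safety need, so the rule tends to remove patients whose later course is informative in a small trial meant to guide Phase 3 titration. Sites also have two sets of instructions. A patient who stops drug for an adverse event is encouraged to stay; the same patient, once unblinded, is by default taken out. Neither 8.1.1 nor 8.2 mentions unblinding, so no other section settles which instruction governs.

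At stake are scheduled safety visits and some HbA1c values in a few patients, and a clear instruction for sites.

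**Working it through.** **1. The provisions side by side.**

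| Protocol section | Trigger | Study participation | Force |
|---|---|---|---|
| 7.3 | Unblinding of investigator, assessing staff or patient | Leave, unless approved to stay | Mandatory, with exception |
| 5.1 | Drug stopped for an AE | Asked to stay | Soft |
| 8.1.1 | Drug permanently stopped | Stay if possible | Soft |
| 8.1.2 | Drug stopped | May stay for all visits | Permissive |
| 9.2.1.2.3 | Drug stopped for hypersensitivity | Should stay | Moderate |
| 9.2.1.2.5 | Pancreatitis supported by tests | Stays | Firm, no approval step |

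The triggers differ. For rows two to five this is a difference of approach, not a contradiction. Row six meets row one only in a pancreatitis patient who is also unblinded. There the two defaults are opposite, and 7.3 adds an approval step that 9.2.1.2.5 lacks.

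**2. Scheduled data lost.** Inputs from the Schedule of Activities: site visits after randomization up to Visit 10 fall on days 7, 14, 28, 56 and 84 (Visits 4, 5, 6, 8, 10). HbA1c is taken on days 28, 56 and 84 and at ET. The Visit 10 window is ±3 days, so it opens on day 84 − 3 = 81. For an exit on day d, visits lost = number of scheduled days after d. Net HbA1c lost = scheduled HbA1c days after d, minus 1 for the ET value, not below 0.

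| Exit | Visits up to Visit 10 replaced by ET | HbA1c values, net of ET | Week 12 HbA1c |
|---|---|---|---|
| Before Visit 4 | 5 | 3 − 1 = 2 | lost |
| Visit 4 to 5 | 4 | 3 − 1 = 2 | lost |
| Visit 5 to 6 | 3 | 3 − 1 = 2 | lost |
| Visit 6 to 8 | 2 | 2 − 1 = 1 | lost |
| Visit 8 to day 80 | 1 | 1 − 1 = 0 | lost |
| Day 81 to Visit 10 | 1 | 1 − 1 = 0 | ET falls in the window |
| After Visit 10 | 0 | 0 | kept |

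Net of the ET visit itself, the visit column is one lower wherever it is above 0. The last column assumes that an ET value counts as Week 12 only inside the window; the SAP does not say how ET values are assigned to visits. Visit 801 is left out for the reason given under the objection.

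**3. Which analyses are touched.**

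- *Primary MMRM on the EAS.* Data beyond last dose + 7 days are excluded whether the patient leaves or stays. The only difference can be a scheduled visit inside that seven-day tail (for example Visit 10 on day 84 after Dose 12 on day 77), and an ET visit in the same days also yields an HbA1c.
- *Supporting MMRM on the FAS.* This would use a later Week 12 value, so this is where the loss falls.
- *Supporting LOCF ANCOVA on the FAS.* This can carry the ET value forward.

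Not every retained value would be informative. Section 8.1.2 allows a switch of diabetes therapy after drug stops, and 7.8.1 ends efficacy collection at rescue.

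**4. Size.** The plan's own figures reproduce: 20 / (1 − 0.13) = 22.99, so 23 per arm and 4 × 23 = 92. With SD 1.1, 20 per arm and a difference of 1.4 − 0.2 = 1.2, the standard error is 1.1 × √(2/20) = 0.348. By normal approximation power is 93.2% at the SAP's two-sided 0.05 and 98.5% at the protocol's one-sided 0.1. The rule changes none of N, alpha or this power.

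One patient is 1/23 = 4.3% of an arm. An assumed 0 to 5 unblinded patients is 0 to 5/92 = 5.4% of the trial, or up to 5/4 = 1.25 per arm on average. As a rough upper bound for an analysis that needs the lost values, going from 20 to 19 per arm lowers power from 93.2% to 92.0%, or 1.2 points. The plan already allows 23 − 20 = 3 dropouts per arm, and such exits may fall within that allowance.

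**The case against.** The strongest reply is that 7.3 answers a different question. Sections 5.1, 8.1.1, 8.1.2 and 9.2.1.2.3 govern stopping drug, mostly in soft wording. The study compares GI tolerability, whose severity and relatedness are judged at the site, so removing unblinded patients protects those assessments. Pancreatitis does not call for a code break, because 9.2.1.2.5 stops drug whatever the assignment, and 7.3 has its own route to stay. Much of this stands: the rule is a defensible choice, and the overlap is narrow. But the aim can be met by stopping drug and marking later assessments, without giving up the visits.

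Three stronger readings are tempting, and the documents do not support them.

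- *The protocol flatly contradicts itself.* Only the overlap of pancreatitis and unblinding gives opposite defaults, and the exception in 7.3 softens even that.
- *Safety follow-up ends on exit.* The ET visit takes HbA1c, safety laboratory tests, antibodies and an ECG, although a local one: "Local ECGs will be collected for screening (Visit 1) and Early Termination". Section 8.2 asks for continued safety follow-up, and 9.2 has serious, related or drug-stopping events followed until they resolve, stabilize or are explained.
- *Section 7.3 cuts off Visit 801.* Section 5.1 words that visit for treatment completers ("All randomized patients who complete the treatment period will complete the safety follow-up approximately 4 weeks after their last visit on treatment") and, for patients unable or unwilling to continue, has "an early termination (ET) visit as their final study visit". But 8.2 refers back to the schedule, whose footnote d reads "Visit should occur 4 weeks after the last dose of study drug or 3 weeks after Visit 10". That uncertainty concerns every early terminator, so it is no argument against 7.3 in particular.

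**Conclusion.** The point holds as a low-priority design comment. By default 7.3 ends participation where ending study drug would do, and it is the only one of these provisions that does so. For an exit before Visit 10, one to five scheduled visits up to Visit 10 are replaced by a single ET visit. For an exit before day 81 the Week 12 HbA1c for the FAS MMRM is also lost. The primary EAS result is unaffected once drug stops, apart from the seven-day tail noted above, and sample size, alpha and planned power do not change.

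The conclusion rests on the texts. Its size rests on an assumed 0 to 5 unblinded patients; the documents give no number, and zero is possible. It also rests on an ET value outside the Visit 10 window not counting as Week 12.

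**What to change.** Reword the rule in 7.3 along these lines: *When the blind is broken for the investigator, for site staff who make assessments or for the patient, study drug is stopped and the patient should stay in the study for the remaining scheduled visits, unless consent is withdrawn. Keeping the patient on study drug needs specific sponsor CRP/CRS approval.* This also removes the opposite defaults in 7.3 and 9.2.1.2.5.

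Record the unblinding date for every case. SAP 7.2 has the IWRS hold it when the IWRS is used, but 7.3 also provides separate emergency codes, and accidental unblinding may bypass both, so an eCRF field is needed as well. Flag site-assessed tolerability events after that date: nausea, vomiting and diarrhea, hypoglycemia relatedness, and injection site reactions. No new EAS exclusion is proposed for patients approved to stay on drug, because HbA1c is measured centrally.

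The cost is a short protocol rewording, one date field and one flag. The downside is that a few patients will have tolerability events assessed with the assignment known; the flag makes those events identifiable.
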